The first objective (**Intervention 1**) will be achieved by comparing whole-body heat storage (measured using combined direct and indirect calorimetry) and the accompanying changes in body temperature (i.e., rectal, mean skin temperature), cardiovascular, and circulating and intracellular inflammatory and stress responses between young and older adults during a 9-hour resting exposure to ~40°C and ~10-15% relative humidity conditions (heat index: 37-38°C). These conditions were chosen to simulate peak temperatures experienced during heatwaves and are similar to conditions in recent heatwaves in North America in 2018 (Ottawa, Ontario; 34°C and 58%, heat index: 41°C) and Europe in 2003 (Paris, France; 38°C and 25%, heat index: 38°C). This intervention will thereby allow for the determination of whether ecologically valid heatwave conditions exceed the physiological capacity for heat dissipation in older adults, and how thermal and cardiovascular strain and inflammation develops during long-duration heat exposure.

The second objective (**Intervention 2**) will be accomplished by comparing physiological responses in the older adults in Intervention 1 to a separate age-matched group removed from the heat to spend 2 hours in a cooler environment (23°C, ~50% relative humidity) approximately mid-way (hours 5-6) through the simulated heatwave. Comparing whole-body heat storage and body temperature, cardiovascular, and inflammatory responses during and after the ambient cooling intervention to the non-cooled group will allow for determination of whether short-term cooling confers prolonged reductions in physiological strain or if the cooling-induced physiological alterations occur only transiently.

Hypotheses

Intervention 1: Age-related attenuation of the human heat loss responses (cutaneous vasodilation and sweating) means that older adults experience greater elevations in body heat storage and body core temperature compared to younger individuals during heat stress. For example, Kenny et al. (*Temperature (Austin)*. 2016 31;4(1):79-88). observed ~80% greater heat storage (equivalent to a ~0.5°C greater elevation in mean body temperature) in middle-aged-to-older compared to young adults during 3-hours of resting heat exposure. More importantly, the middle-aged-to-older adults did not achieve a state of heat balance (i.e., they were still storing heat within their body at the end of the 3 hours).

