Based on this work, our primary hypothesis is that older adults will not achieve a state of heat balance (i.e., rate of heat loss balancing the rate of heat gain; thermal equilibrium) and therefore experience greater heat storage throughout the 9-hour simulated heatwave compared to the younger participants. Consequently, body core temperature will be greater in the older adults and between-group differences will be exacerbated as exposure progresses. We will also explore the secondary hypothesis that differences in body temperature will be paralleled by greater alterations in cardiovascular variables and circulatory and intracellular markers of acute inflammation and stress in the older adults.

Intervention 2: Our primary hypothesis is that body heat storage will be exacerbated in the older adults exposed to the cooling centre intervention upon return to the heat (hours 5-6) compared to the older adults from Intervention 1 who remained in the heat. Consequently, body core temperature will be comparable (statistically equivalent) between groups by the end of exposure (i.e., 9 hours, 3 hours after return to the heat). This is because body temperature is regulated through a negative feedback mechanism. Elevations in core and skin temperatures elicit proportional activation of cutaneous vasodilation and sweating to facilitate heat loss and stabilize body temperature. Thus, core and skin cooling will suppress heat loss and, upon return to a hot environment, heat will be rapidly gained until body temperature rises to an extent sufficient to activate heat loss and re-attain thermal equilibrium. We will also evaluate the secondary hypothesis

that, in parallel to body core temperature, any effect of cooling on cardiovascular responses and acute inflammation will be abated by the end of the heat event.

METHODS

Participants

A total of 20 young (age: 18-30 years) and 40 older (age: 64-80 years) adults will be recruited for the project. Young (n=20) and older (n=20) adults will be recruited for **Intervention 1** and a separate cohort of older adults (n=20) for **Intervention 2**. Details on the determination of the sample sizes for each intervention are provided below.

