Written and informed consent will be obtained from all volunteers prior to participation. Recruited participants will be homogenous for anthropomorphic characteristics and habitual physical activity levels as verified via standardized questionnaires and each intervention will have an approximately even distribution of males and females. Older participants will be screened for cardiovascular risk factors prior to the heatwave simulations. No participants will be current smokers. The specific inclusion and exclusion criteria for the study are provided below

Inclusion Criteria

- Male or female (non-pregnant) adults with or without a) chronic hypertension (elevated resting blood pressure; as defined by Heart and Stroke Canada and Hypertension Canada), b) type 2 diabetes as defined by Diabetes Canada, with at least 5 years having elapsed since time of diagnosis and or c) obesity as defined by the World Health Organization (Body Mass Index [BMI] greater than or equal to 30).
- Non-smoking.

Exclusion Criteria

- Episode(s) of severe hypoglycemia (requiring the assistance of another person) within the previous year, or inability to sense hypoglycemia (hypoglycemia unawareness).
- Serious complications related to diabetes (gastroparesis, renal disease, uncontrolled hypertension, severe autonomic neuropathy).
- Uncontrolled hypertension – Arterial blood pressure >150 mmHg systolic or >95 mmHg diastolic in a sitting position.

- Restrictions in physical activity due to disease (e.g. intermittent claudication, renal impairment, active proliferative retinopathy, unstable cardiac or pulmonary disease, disabling stroke, severe arthritis, etc.).
- Use of or changes in medication judged by the patient or investigators to make participation in this study inadvisable.
- Cardiac abnormalities identified in your physical health screening forms (adults <65 years of age and older; adults <60 years of age and older with diabetes and or hypertension) or during exercise stress testing as assessed by 12-lead (all adults ≥65 years of age and older).

Sample size calculations

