Intervention 1: An *a priori* power analysis determined that a total sample size of 19 young and 19 older adults is required to detect a difference in the rate of whole-body heat storage between groups at the end of each calorimeter session (i.e., hours 3 and 9) with 80% statistical power. In lieu of clinically meaningful data (i.e., what would be considered a clinically meaningful change in whole-body heat storage), the standardized effect size (Cohen's $d = 1.06$) was calculated from the difference in the rate of body heat storage between young and older adults over the final 30-min of a 3-hour heat exposure (young: -2 [26] kJ/hour, older: 43 [54] kJ/hour) in our previous work (Kenny et al. *Temperature (Austin)*. 2016 31;4(1):79-88).

Intervention 2: An *a priori* power analysis determined that a total sample size of 18 older adults in each group is required to confirm whether between-group differences in rectal temperature are within upper and lower bounds of +0.3°C and -0.3°C, respectively, with 80% power. This corresponds to an effect size (Cohen's d) of 1.0, based on the pooled-standard deviation of 0.3°C. Equivalence bounds were chosen based on the typical day-to-day variation of body core temperature (Consolazio et al. *Physiological measurements of metabolic functions in man*. 1963:453-480) and suggested meaningful/detectable change in body core temperature in a recent study assessing the influence of personal cooling strategies on physiological strain in young adults (Morris et al. *Annals of Internal Medicine*. 2019;171(9):675-677). The standard deviation for the between group difference was determined from data from our laboratory demonstrating a 0.2°C (SD 0.3) difference in rectal temperature between young and older adults (Kenny et al.

Temperature (Austin). 2016;4(1):79-88) and a 0.0°C (SD 0.3) difference between older adults with and without type 2 diabetes (Poirier et al. *Temperature (Austin)*. 2020;7(3):263-269) during 3 hours of rest in the heat (44°C, 30% relative humidity).

Experimental Design

Pre-trial instructions

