The effect of the cooling intervention on cumulative whole-body heat storage over the 3 hours following return to the heat will be evaluated using a linear mixed-effects model with experimental group (two levels: cooling and no-cooling) modelled as a between-subject fixed effect. Cumulative heat storage over the first three hours of the 9-hour exposure will be included as a covariate to account for the influence of any inter- or intra-individual factors (e.g., sex, physical activity levels), measured or unmeasured, impacting whole-body heat exchange and storage. Comparisons of heat storage between groups will be made using model estimated marginal means.

Body core temperature (primary outcome)

Body core temperature, as estimated by rectal temperature, will be analyzed with a linear mixed effects model with experimental group (two levels: cooling and no-cooling) modelled as a between-subject fixed effect and time as a repeated within-subject fixed effect (0-, 1-, 2-, and 3-hours post-cooling intervention). Like the model for heat storage, rectal temperature at the end of the first calorimetry session (i.e., hour 3 of the 9-hour exposure) will be included as a covariate to account for the influence of any measured or unmeasured inter- or intra-individual factors impacting the body temperature responses to resting heat exposure.

Because this study was designed to assess the hypothesis that body core temperature will be similar (equivalent) between groups following return to the heat, the effect of cooling on rectal temperature will be assessed via two one-sided tests (see Lakens. *Soc Psychol Personal Sci.* 2017:8 (4), 355-362) performed on the mixed-effects model derived estimated marginal means at each timepoint. For the equivalence testing, the null hypothesis is taken as a meaningful difference between groups and its rejection therefore

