corresponds to an equivalence of means. These are presented alongside the results of a traditional Welch's t-test. This permits evaluation of both statistical differences, and statistical equivalencies in physiological responses. Performing analysis on the marginal means will allow for isolation of the effect of cooling from individual differences in the body temperature response to heat exposure (captured in the 3-hour timepoint covariate). Equivalence bounds will be set to $\pm 0.3^{\circ}\text{C}$, which corresponds to the typical day-to-day variation of core temperature (Consolazio et al. *Physiological measurements of metabolic functions in man*. 1963:453-480) and has been suggested to reflect a meaningful/detectable change in body temperatures in a recent study assessing the influence of cooling strategies on physiological strain in young adults (Morris et al. *Annals of Internal Medicine*. 2019;171(9):675-677).

Secondary outcomes

Mean skin temperature as well as cardiovascular responses and circulating/intracellular inflammatory/stress markers will be modeled with linear mixed-effects models. The analyses for mean skin temperature and cardiovascular responses will be performed similar to that for rectal temperature except only two time points will be included (0- and 3-hours post-cooling intervention). Circulating and intracellular changes in inflammatory markers, measured at the start and end of exposure only, will be analyzed with a linear mixed-effects model with age-group (two levels: young and older adults) modelled as a between-subject fixed effect, and participant sex, self-reported and weekly physical activity (min/week, as assessed via the GAQ), included as covariates.

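### Does the unstated input to the Welch test undermine the Intervention 2 rectal temperature comparison?

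*Combined protocol and SAP*

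**What the plan says.** The SAP subsection on body core temperature (Intervention 2) specifies a mixed model with group, time (0, 1, 2 and 3 hours after cooling) and hour-3 rectal temperature as covariate. Two one-sided tests against ±0.3°C are applied to the model's marginal means at each timepoint. The next statement is "These are presented alongside the results of a traditional" Welch's t-test, with the aim of giving both a difference verdict and an equivalence verdict. The SAP then explains that working on marginal means separates the effect of cooling from individual variation carried by the hour-3 value.

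The heat-storage subsection is more explicit: "Comparisons of heat storage between groups will be made using model estimated marginal means". The closing paragraph on all Intervention 2 models plans 90% intervals for equivalence and 95% intervals for significance testing.

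On design, the Objectives describe "comparing physiological responses in the older adults in Intervention 1 to a separate age-matched group", and the Participants section says "Recruited participants will be homogenous for anthropomorphic characteristics and habitual physical activity levels". The hour-3 temperature is included "to account for the influence of any measured or unmeasured inter- or intra-individual factors impacting the body temperature responses"; the heat-storage covariate is justified in similar terms, by factors "measured or unmeasured, impacting whole-body heat exchange and storage".

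**The concern.** A Welch test in its ordinary form takes two samples and no covariate. The word traditional can therefore be read as a test on raw rectal temperatures, set beside an equivalence test on adjusted means. The two verdicts on one primary outcome would then come from different estimates with different standard errors.

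Two consequences would follow. The difference test would be the weaker one, so a real residual effect of cooling inside ±0.3°C could be missed. And because the cohorts are recruited separately, with no random allocation described in the available text, an hour-3 imbalance could produce a significant raw difference that cooling did not cause.

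The SAP also states that it was submitted after analysis of the full data set, though before unblinding, which makes an open choice of test input less comfortable. The covariate rationale invites a related doubt: an hour-3 value can adjust only for differences already expressed by hour 3, and the limitations section does not mention the between-cohort comparison.

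**Working it through.** **1. Reading the text in order.** The equivalence tests are placed on marginal means. The Welch test is set alongside them so that both verdicts can be given. The marginal-means rationale comes after both tests have been introduced and is not confined to one. In that order, traditional most naturally contrasts a null-hypothesis test with an equivalence test. The heat-storage comparison and the Intervention 1 post hoc comparisons also use marginal means. The 95% intervals planned for significance testing point the same way, although the contrast they belong to is not named.

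**2. The plan's own figure.** Inputs from the Intervention 2 sample size section are bounds of ±0.3°C, 80% power and "based on the pooled-standard deviation of 0.3°C". With a true difference of 0 and 5% for each one-sided test:

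n = 2 × ((1.645 + 1.282) × 0.3/0.3)² = 17.13, rounded up to 18 per group.

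This matches the stated 18. Exact power is 80.5% at 18 and 85.6% at the planned 20. The Welch test plays no part in this.

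**3. Marginal-means reading.** Take a single-timepoint analysis of covariance as a stand-in for the model contrast. Let n be the size of each group, Δ the hour-3 imbalance, Sxx the pooled within-group sum of squares of hour-3 temperature, and s² the residual variance.

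- Model contrast variance: s²(2/n + Δ²/Sxx)
- Sum of the two marginal-mean variances, as a Welch-type formula would use: s²(2/n + Δ²/(2Sxx))

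They differ only by a small covariance term. With n = 20, an assumed hour-3 SD of 0.3°C (Sxx ≈ 38 × 0.09 = 3.42) and Δ = 0.10°C, Δ²/Sxx = 0.01/3.42 = 0.0029. The ratio of standard errors is √(0.10146/0.10292) = 0.993. Simulation gives a median ratio of 0.997 with no systematic imbalance (5th percentile 0.975) and 0.992 with a 0.10°C imbalance (5th percentile 0.956).

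**4. Raw reading.** The documents do not give the hour-3 to hour-9 correlation r, so 0.3 to 0.8 is assumed. The raw standard error is 0.3 × √(2/20) = 0.095°C; the adjusted one is this times √(1 − r²). Simulation used 100,000 trials per setting, n = 20 per group, SD 0.3°C and equal variances:

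| | r = 0.3 | 0.5 | 0.7 | 0.8 |
|---|---|---|---|---|
| Adjusted SE (°C) | 0.091 | 0.082 | 0.068 | 0.057 |
| Power at 0.20°C, raw Welch | 54% | 54% | 54% | 54% |
| Power at 0.20°C, adjusted | 57% | 65% | 81% | 92% |
| Disagreement at true difference 0 | 3% | 5% | 6% | 8% |
| False positives, raw, imbalance 0.10°C | 6% | 8% | 11% | 13% |
| False positives, raw, imbalance 0.05°C | 5% | 6% | 6% | 7% |

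The adjusted test stays at about 5% false positives throughout.

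**5. Paired verdicts at a true 0.20°C, raw reading, no imbalance.** Equivalent and not different: 28% with raw Welch against 27% with the model contrast at r = 0.5, 30% against 18% at 0.7, and 33% against 8% at 0.8. Neither equivalent nor different: 19% against 8%, 16% against 0.5%, and 13% against under 0.1%. The shift towards equivalent and not different is therefore negligible at moderate r and large only at 0.7 to 0.8.

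**6. The covariate wording.** The hour-3 value precedes cooling and is a valid covariate whatever is claimed for it. Rewording the rationale, or adding a limitation about cohorts already described as separate, would change no estimate, interval or test.

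**The case for a change.** The strongest case for a change is that the SAP should not leave a primary-outcome test to inference. Marginal means carry a model-based standard error and degrees of freedom, so a Welch test on them is not strictly defined. Two competent analysts could report different p-values. On the raw reading at 0.20°C, the two difference tests disagree in 10%, 19%, 32% and 41% of trials at r = 0.3, 0.5, 0.7 and 0.8. The issue might carry over to mean skin temperature and cardiovascular outcomes, which are analysed like rectal temperature and for which a lasting effect of cooling is the focus. Naming the contrast would cost one sentence, and the late submission of the SAP makes written precision more valuable.

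What stands is the literal point: the input is not named, and a raw Welch result, if reported, should be labelled unadjusted. The rest carries less weight. The disagreement figures belong to the less natural reading and to values of r and of the true difference that the documents do not supply. Carry-over is uncertain, since the secondary-outcomes text specifies mixed models and does not mention Welch. The late submission does not affect the equivalence test, whose input and bounds are fully stated. Replacing the Welch test outright would go further than the gap, and the simulation assumes equal variances, so it does not examine the setting for which Welch is usually chosen.

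**Conclusion.** The concern does not call for a change. The SAP omits a detail that its surrounding sentences and planned intervals supply. An analyst who follows them takes the difference result from the hour-3-adjusted marginal means, where the choice between a Welch-type and a model standard error moves it by under 1% at the median.

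The inference for which Intervention 2 was designed and sized is equivalence within ±0.3°C. That result, and the 18 per group, are identical on either reading.

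A material loss needs the raw reading together with conditions outside the documents: r of about 0.7 to 0.8 with a true difference of 0.15 to 0.20°C, or an hour-3 imbalance near 0.10°C. The figures rest on a single-timepoint stand-in for the mixed model, an hour-3 SD of 0.3°C and equal variances. The points about covariate wording and limitations alter no result.

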Statistical analysis for **Intervention 1** will compare whole-body heat storage and the resultant progression of body temperature, cardiovascular and acute inflammatory responses between the young and older adults during the simulated heatwave. Whole-body heat storage (primary outcome), body temperature responses including rectal temperature (primary outcome) and mean skin temperature (secondary outcome), as well as cardiovascular responses (secondary outcomes) will be evaluated using linear mixed-effects models. Time will be modelled as a repeated within-subject fixed effect (two levels: 3 and 9 hours), and age-group (two levels: young and older adults) will be modelled as a between-subject fixed effect. Pre-heat exposure values of the outcome variable, participant sex, and self-reported weekly physical activity (min/week, as assessed via the GAQ) will be included as covariates. Circulating and intracellular markers of acute inflammation and stress (secondary outcomes) will be evaluated using a similar model but without the fixed effect of time (data was only collected at the end of exposure) and baseline values included as a covariate (where appropriate). Participant identification will be modeled as a random effect in all analyses. Akaike's information criterion will be used to determine random effect and variance/covariance structures.

Post hoc multiple comparisons will be made on model estimated marginal means. Given the small number of comparisons for each variable, multiplicity corrections will not be employed. Homoscedasticity will be evaluated for all models by visual assessment of residual plots. Approximate normal distribution of residuals will be assessed via visual inspection of histograms and Q-Q plots. Data will be log-transformed in the event that the distribution of residuals meaningfully deviates from normality. For all analyses, the level of significance will be set at $P < 0.050$. Descriptive statistics will be presented as means and standard deviations. Comparisons between groups and/or time-points will be presented as means and 95% confidence intervals [lower limit, upper limit].

Intervention 2

Statistical analysis for Intervention 2 will evaluate the acute and lasting impacts of the short-term cooling intervention (i.e., during cooling and following return to the heat, respectively) on physiological responses.

Cumulative heat storage (primary outcome)

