The analysis of secondary variables will focus on whether there was a lasting effect of cooling 3 hours following return to the heat. However, we will also perform tertiary exploratory analysis to evaluate whether the end-exposure responses are similar (equivalent) within pre-specified bounds. Describing clinically meaningful bounds in this context is complex since there is little research regarding how the risk of adverse health events changes with *acute* alterations in cardiovascular responses or inflammatory status during heat exposure (or cooling). For heart rate (± 5 beats/min) and rate pressure product (± 1500 beats/min), the equivalence bounds for these exploratory analyses will be based on meaningful/detectable differences employed in recent studies evaluating the efficacy

of personal cooling strategies in laboratory-based studies (Morris et al. *Annals of Internal Medicine*. 2019;171(9):675-677). For arterial blood pressure responses, we will consider ± 5 mm Hg an appropriate clinically meaningful bound, given the associated 9%, 13%, and 6% reduction in risk of myocardial infarction, stroke, and mortality (Psaty et al. *Arch Intern Med*. 2001;161(9):1183-1192). For the other variables, reasonable equivalence bounds are not forthcoming. We will therefore set the bounds for these outcomes at ± 1 SD of the between-group difference (based on our sample size determination).

For all models, participant identification will be modeled as a random effect and Akaike's information criterion will be used to determine random effects and variance/covariance structure. The level of significance will be set at $P < 0.050$. Descriptive statistics will be presented as mean (standard deviation). Both 90% confidence intervals and 95% confidence intervals will be computed to facilitate interpretation of the equivalence testing and null hypothesis significance testing (respectively).

As noted at the start of the document, the statistical analysis plan was submitted after cleaning and analysis of the full data set, but prior to unblinding of the data.

Delimitations and limitations

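### The Intervention 2 inflammatory and stress-marker model uses age group as its factor and has no cooling term, so it cannot estimate the cooling effect

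*Combined protocol and SAP*

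**What the plan says.** The Intervention 2 part of the statistical analysis plan opens with its purpose: "Statistical analysis for Intervention 2 will evaluate the acute and lasting impacts of the short-term cooling intervention". Both primary models in that part, for cumulative heat storage and for rectal temperature, have "experimental group (two levels: cooling and no-cooling) modelled as a between-subject fixed effect".

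The Secondary outcomes paragraph then treats two sets of variables differently. For the first set, "The analyses for mean skin temperature and cardiovascular responses will be performed similar to that for rectal temperature", so these variables inherit the cooling factor. The circulating and intracellular markers get a separate specification: a "linear mixed-effects model with age-group (two levels: young and older adults) modelled as a between-subject fixed effect", with sex and weekly physical activity as covariates.

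The hypothesis this model should serve is in the Hypotheses section. For Intervention 2 the secondary hypothesis is that "any effect of cooling on cardiovascular responses and acute inflammation will be abated by the end of the heat event". The SAP adds that the secondary analyses concentrate on a lasting cooling effect, and that end-exposure responses will also be tested for equivalence as an exploratory step. Variables without their own bound are given ±1 SD.

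On numbers, the Participants section states: "A total of 20 young (age: 18-30 years) and 40 older (age: 64-80 years) adults will be recruited for the project". The 40 older adults are two groups of 20, one remaining in the heat and one cooled.

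**The concern.** The group factor in the marker model does not match the comparison that Intervention 2 was set up to make. Both Intervention 2 groups are older adults, so age group does not separate them, and nothing else in the listed fixed effects does.

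An analyst who follows the text literally has no cooling result for any inflammatory or stress marker. With only the older adults in the data, the error shows itself because the factor has one level. With the young adults also in the data, the model fits without complaint and returns an age contrast under a cooling heading, which is easier to miss. An analyst who substitutes the evident factor without saying so departs from the written plan. That matters somewhat more here because the SAP states that it was submitted after the full data set had been cleaned and analysed, though before unblinding, so its wording is the record against which the report will be read.

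**Working it through.** The only sample-size figure for Intervention 2 is 18 per group for rectal-temperature equivalence (bounds ±0.3°C, SD 0.3°C, 80% power). It reproduces: 2 × (1.645 + 1.282)² × (0.3/0.3)² = 17.13, rounded up to 18. It has no bearing on the marker model. The check is whether the stated fixed effects contain a cooling contrast.

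**Step 1. Is a cooling term supplied elsewhere?**

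| Place in the SAP | What it covers | Cooling term for the markers? |
|---|---|---|
| Intervention 1 | Young versus older: "age-group (two levels: young and older adults) will be modelled as a between-subject fixed effect" | No |
| Intervention 2, primary outcomes | Heat storage and rectal temperature only | No |
| Intervention 2, Secondary outcomes, first model | Skin temperature and cardiovascular responses only | No |
| Intervention 2, rule for all models: "For all models, participant identification will be modeled as a random effect" | Participant random effect and use of Akaike's criterion | No |

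The factor wording in the marker model closely matches the Intervention 1 wording, which suggests that it was carried over. That is an inference.

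**Step 2. Is the cooling effect estimable?** As written, the mean for participant *i* is

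b0 + b1·age group(i) + b2·sex(i) + b3·activity(i).

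Two older adults of the same sex and activity level have the same fitted mean whether or not they were cooled. In terms of design-matrix rank, with sex varying and activity continuous:

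- *40 older adults, as written.* Age group is constant and aliased with the intercept: 4 columns, rank 3. The age coefficient is not estimable and there is no cooling contrast.
- *All 60 participants, as written.* 4 columns, rank 4. The model fits, but b1 is older minus young. Adding a cooling indicator raises the rank to 5, so cooling lies outside the written model.
- *40 older adults, experimental group in place of age group.* 4 columns, rank 4. The cooling coefficient is estimable.

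**Step 3. How many analyses are affected?** The section on circulating and intracellular markers lists three in serum (TNF-alpha, IL-6, CRP) and four in cells (HSP70, HSP90, TNF-alpha, IL-6): 3 + 4 = 7. Each has one cooling comparison and one exploratory equivalence analysis: 7 + 7 = 14. The sentence giving the model says only inflammatory markers, although the paragraph opens with inflammatory and stress markers together. Leaving out the two heat-shock proteins gives 5 markers and 5 + 5 = 10 analyses. Those two proteins would then have no Intervention 2 model at all, so no marker has a cooling term on either count.

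**The case against.** The best defence is that the intent is not in doubt. The opening of the Intervention 2 section, the secondary hypothesis, the primary models and the statement that follows the faulty sentence all point to cooling versus no cooling. There is one plausible correction and little analytic freedom in making it. The outcomes are secondary or exploratory. This stands as a limit on seriousness, but it does not make the written rule correct.

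Three further points qualify the finding:

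- *Timing.* The documents do not show which model was fitted, and the analysis may already have been done. Whether a repair would go unrecorded is therefore unknown, and the point does not depend on it.
- *Rank.* The rank result for the 40 older adults only formalises the fact that a constant is constant. The substance is the missing cooling term, and the 60-participant reading shows that it matters even when the model fits.
- *Outcome form.* The sentence speaks of changes in markers, and also of measurement at start and end. If both values were entered as rows, swapping the factor without a time or group-by-time term would average the group effect over baseline and end. If one change per person is analysed, the swap gives the intended contrast, although a participant random effect is then not separable from the residual. The plain reading is one change per person, and the correction rests on it.

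**Conclusion.** The concern holds. As written, the Intervention 2 marker model contains no cooling contrast, whether it is fitted to the 40 older adults or to all 60 participants. It affects 7 markers and 14 secondary or exploratory analyses (5 and 10 on the narrowest reading). The equivalence count assumes that the markers fall among the variables given ±1 SD bounds, since the SAP does not list them there by name.

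The two primary models and the skin-temperature and cardiovascular models carry the right factor and are unaffected. No sample size, power or significance level changes. The sentence should be corrected, but it does not threaten the main conclusions of the study.

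**What to change.** In the marker model under Intervention 2, Secondary outcomes, replace the age-group factor with the one used for the Intervention 2 primary outcomes, "experimental group (two levels: cooling and no-cooling) modelled as a between-subject fixed effect", and state that the model is fitted to the 40 older adults. Leave the outcome (the change in each marker) and the covariates as they stand. Because of when the SAP was submitted, enter this as a dated wording correction.

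The cost is one phrase, one clause naming the analysis set and a dated note. No new data, participants, covariates or tests are needed.
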